A safety assessment (ECG, vital signs, laboratory) is considered treatment-emergent, if the assessment date is on or after the study treatment start date and prior to or on the study treatment end date + 15 days (inclusive). If both, the assessment date/time and the date/time of study treatment start are available, only events with date/time on or after the date/time of study treatment start are considered to be treatment-emergent. In case of (partially) missing assessment dates/times, or for assessments on treatment Day 1 with reported assessment time contradicting the timepoint label, the nominal visit and timepoint labels will be used to determine whether an assessment is considered as treatment-emergent or not. For example, a blood pressure measurement with an assessment date on Day 1 but a missing assessment time or an assessment time after the time of first study drug intake, will not be considered treatment-emergent if reported under the timepoint “Pre-dose” in the eCRF, however it will be considered if reported as “2 hours post-dose” in the eCRF.

A safety event (AE, serious AE [SAE], Death) is considered treatment-emergent if the onset date/date of occurrence is on or after the study treatment start date and prior to or on the EOT date + 15 days (inclusive). Missing or partially missing onset or occurrence dates are imputed as described in Section 12.3. If both the onset/occurrence date/time and the date/time of study treatment start are available, only events with date/time on or after the date/time of study treatment start are considered to be treatment-emergent.

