5.5.11.2 Qualitative ECG variables

Morphological ECG findings are reported by the central reader, and mapped to CDISC standard (codelist C71150, with high level categories from codelist C71152) in the SDTM.

For analyses in tables the following categories are anticipated:

- Atrioventricular Conduction
- Axis and Voltage
- Chamber Hypertrophy or Enlargement
- Conduction
- Ectopy
- Intraventricular-Intraatrial Conduction
- Rhythm Not Otherwise Specified
- ST Segment, T wave, and U wave
- Sinus Node Rhythms and Arrhythmias
- Supraventricular Arrhythmias
- Supraventricular Tachyarrhythmias
- Ventricular Arrhythmias

Findings related to interpretation or technical issues are only included in listings.

Morphological ECG findings are flagged as “New” if not present at any pre-treatment assessment (i.e., at any ECG assessed prior to the study treatment start) or “Pre-existing” if present at any pre-treatment assessment. In case of missing or non-evaluable pre-treatment ECG assessment, it is conservatively assumed that any treatment-emergent morphological ECG finding is “New”.

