9.9.3 Electrocardiography (ECG)

The following summary displays are provided by treatment group, all based on the SAF:

- Quantitative ECG results and absolute change from baseline, as described in Section 5.5.11.1, are summarized descriptively, by parameter and visit. Except for data summarized under ‘Baseline’, ‘last-on-treatment’ and ‘Day-30 follow-up’, only treatment-emergent results from nominal scheduled visits are included, premature EOT visit is mapped to a scheduled visit [see Section 11.3];
- Quantitative ECG results and absolute change from pre-dose on Day 1, by timepoint (pre-dose, 1–4 hours post dose), are summarized descriptively;
- Number and percentage of subjects with any treatment-emergent PR, QTcF prolongations and HR outliers are presented overall. Percentages are based on the number of subjects with at least one treatment-emergent result available for the corresponding parameter. Abnormalities are presented cumulatively, i.e., a subject with a treatment-emergent QTcF result > 500 ms is also summarized in the category QTcF > 450 ms;
- Number and percentage of subjects with any 3-hr post-dose PR, QTcF prolongations and HR outliers on Day 1, Week 12 Visit, and Day 1 of any re-initiation. For this analysis the ECG results reported as 3-hours post-dose are considered, irrespective of actual time the ECG was performed. Percentages are based on the number of subjects with a result available for the corresponding parameter at 3-hours post-dose. Abnormalities are presented cumulatively;
- Number and percentage of subjects with new treatment-emergent morphological ECG findings, by abnormality and group term following CDISC terminology are presented;
- Number and percentage of subjects with new treatment-emergent post-dose morphological ECG findings on Day 1 or on Day 1 of any re-initiation, by abnormality and group term following CDISC terminology are presented.

All ECG data including QTc parameters are listed by treatment group and subject based on the SCR. All marked abnormalities are flagged and morphological findings are listed.

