9.9.5 Laboratory tests

Descriptive summary statistics by visit and treatment group are provided for laboratory test results reported by the central laboratory and corresponding absolute changes from baseline, based on the SAF. Except for 'Baseline', 'Last on treatment' and 'Day-30 follow-up', only treatment-emergent results from nominal scheduled visits are included; premature EOT visit is mapped to a scheduled visit [see Section 11.3]. Data are displayed in SI units as provided by the central laboratory. Values from unscheduled visits are not included in by visit summaries but are included in the listings and in the summaries for marked abnormalities and liver function test abnormalities.

For lymphocyte counts, this table is also provided on percent changes from baseline. The number of subjects with at least one treatment-emergent marked laboratory abnormality is summarized by treatment group, based on the SAF. The worst case in each direction is considered and summarized in all applicable categories, i.e., a subject counted in LLL is also counted in LL for a given parameter; also, a subject maybe counted in both the high and the low category for a given parameter. In addition, the number of subjects with treatment-emergent liver function test abnormalities is summarized by treatment group. The denominator for percentages is the number of subjects with at least one post-baseline assessment.

Safety laboratory hematology, clinical chemistry, urinalysis parameters planned as per protocol are also presented in subject data listings based on the SCR. All abnormalities and marked abnormalities including those at baseline are flagged in the listings.

A shift table of the frequency counts and percentages of number of subjects with positive, negative and indeterminate results at baseline and at EOS for JCV serology will be presented separately.

Other laboratory parameters are presented in a separate listing on the SCR.

Further analyses related to lymphocytes and lymphocyte subsets are described in Section 9.10.

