9.9.6 Pulmonary function tests - Spirometry

The following summary displays are provided by treatment group, all based on the SAF:

- Treatment-emergent FEV1, FVC, FEV1/FVC, %predFEV1, and %predFVC including absolute and percent change from baseline, as described in Section 5.5.13.1, are summarized descriptively, by parameter and visit. Except for ‘Baseline’, ‘Last on treatment’ and ‘Day-30 follow-up’, only treatment-emergent results from nominal scheduled visits are included; premature EOT visit is mapped to a scheduled visit [see Section 11.3].
- Number and percentage of subjects with any occasion of treatment-emergent low spirometry values as defined in Section 5.5.13.1 are presented. Percentages are based on the number of subjects with at least one treatment-emergent result available for the corresponding parameter;

All spirometry results are listed by treatment group and visit based on the SCR. A listing of spirometry data in subjects with treatment-emergent decrease ≥ 0.2 L or $\geq 12\%$ in FEV1 (or FVC) is also presented.

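### For absolute-threshold safety flags, the timing-only definition of treatment-emergent counts abnormalities already present before first dose, and no summary table separates them from new ones

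*SAP*

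**What the plan says.** **Definition (SAP 5.5.1).** "A safety assessment (ECG, vital signs, laboratory) is considered treatment-emergent, if the assessment date is on or after the study treatment start date", with the window closing 15 days after the last dose. Clock time is used when available. When dates or times are missing, or conflict with the timepoint label on Day 1, "the nominal visit and timepoint labels will be used to determine whether an assessment is considered as treatment-emergent or not". All of these rules concern timing.

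**Tables that use it.**
- 9.9.5, laboratory: "The number of subjects with at least one treatment-emergent marked laboratory abnormality is summarized by treatment group, based on the SAF".
- 9.9.5, liver: "the number of subjects with treatment-emergent liver function test abnormalities is summarized by treatment group". For percentages, "The denominator for percentages is the number of subjects with at least one post-baseline assessment".
- 9.9.3, ECG: "Number and percentage of subjects with any treatment-emergent PR, QTcF prolongations and HR outliers are presented overall".
- 9.9.4, blood pressure: subjects with any treatment-emergent result meeting the 5.5.10.1 criteria.
- 9.9.6, spirometry: "Number and percentage of subjects with any occasion of treatment-emergent low spirometry values as defined in Section 5.5.13.1 are presented".

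**Where the SAP does separate new from old.** In 5.5.11.2 an ECG morphology finding is called new "if not present at any pre-treatment assessment (i.e., at any ECG assessed prior to the study treatment start"), and a missing pre-treatment ECG makes any finding new. In Appendix C the high hemoglobin flags switch to change from baseline when baseline is above ULN. Shift tables are planned for JCV serology (9.9.5) and the eC-SSRS (9.9.7), but for no other laboratory or liver result.

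**The concern.** The safety question is what ponesimod adds to DMF. A table headed treatment-emergent is normally read as showing what appeared or worsened after the add-on started. For an absolute limit with no baseline condition, the planned count mixes two groups: subjects who crossed the limit on treatment, and subjects who were over it before first dose and remained so. The denominators do not exclude the second group. Carried-over cases say nothing about the add-on. They raise the percentage in both arms, narrow the contrast and add noise in a study of 136 randomized subjects. The ECG morphology rule shows that the SAP's authors had the distinction in hand. Within 9.9.3 itself, morphology is reported as new treatment-emergent, while heart-rate and QTcF outliers are only treatment-emergent.

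**Working it through.** **Step 1: sort the flags by whether baseline enters the criterion.**

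| Group | Flags | Can a carried-over case be counted? |
|---|---|---|
| Liver (5.5.12.1) | ALT and AST from 1 to 20 x ULN, bilirubin 2 x ULN, the combinations | Yes |
| Table 9 (Appendix C) | Most parameters, such as glucose > 8.9, triglyceride > 3.42, cholesterol > 7.75 mmol/L | Yes |
| Heart rate (5.5.11.1) | 50, 45 and 40 bpm or lower | Yes |
| QTc, stand-alone | > 450, > 480, > 500 ms | Yes |
| Blood pressure, stand-alone (5.5.10.1) | SBP 90 or lower, 140 or higher, 160 or higher; DBP 50 or lower, 90 or higher, 100 or higher | Yes |
| FEV1/FVC (5.5.13.1) | < 70% | Yes |
| Creatinine | Multiple of ULN or multiple of baseline | In part: either limb suffices |
| PR | > 200 ms and an increase > 20 ms | No |
| QTc and blood-pressure change | Increase or decrease from baseline | No |
| FEV1, FVC and their % predicted | Change from baseline | No |
| Hemoglobin HH/HHH, baseline above ULN | Increase from baseline | No |

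**Step 2: size of the effect.** The SAP states no baseline prevalence and no expected abnormality rate, so there is no figure of its own to reproduce. What follows is an illustration.

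Let b be the share of each arm over the limit at baseline and again on treatment, and p the new-onset risk among the rest.

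- Reported rate = b + (1 - b)p
- Reported difference = (1 - b)(p1 - p0)
- Share of reported cases that are carried over = b / reported rate

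Assume p = 10% on ponesimod and 5% on placebo. For b = 3%: 0.03 + 0.97 x 0.10 = 0.127 and 0.03 + 0.97 x 0.05 = 0.0785. For b = 10%: 0.10 + 0.90 x 0.10 = 0.190 and 0.10 + 0.90 x 0.05 = 0.145. The other rows follow in the same way.

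| b | Reported, ponesimod | Reported, placebo | Difference (points) | Carried-over share of placebo cases |
|---|---|---|---|---|
| 0% | 10.0% | 5.0% | 5.00 | 0% |
| 1% | 10.9% | 6.0% | 4.95 | 17% |
| 3% | 12.7% | 7.9% | 4.85 | 38% |
| 10% | 19.0% | 14.5% | 4.50 | 69% |
| 20% | 28.0% | 24.0% | 4.00 | 83% |

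**Step 3: noise.** Take 68 per arm (136 / 2, assuming the planned 1:1 allocation held and all were treated). At b = 10% the standard error of the reported difference is sqrt((0.190 x 0.810 + 0.145 x 0.855) / 68) = 6.4 points. Restricting to subjects below the limit at baseline leaves 0.90 x 68 = 61.2 per arm, and the standard error is sqrt((0.10 x 0.90 + 0.05 x 0.95) / 61.2) = 4.7 points.

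**The case against.** The case for leaving the plan alone has real weight.

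- **The term is defined and followed.** Section 5.5.1 says what it means, and pre-dose results are never counted. A window-based count is a disclosed convention. This stands: the count is not an error against the SAP's own definition. What the tables lack is the means to tell new from old.
- **Baseline enters in many other places.** Besides the flags marked No above, by-visit change-from-baseline summaries are planned for laboratory, ECG, blood-pressure and spirometry results, and the laboratory listings flag baseline abnormalities. This also stands, but a mean change does not show which outlier subjects are new, and a listing leaves the reader to count by hand.
- **Entry criteria limit baseline abnormality.** The deviation list refers to protocol criteria on lymphocytes, hematology, liver values, cardiovascular and pulmonary conditions. The cut-offs are not in the SAP, but severe categories are probably rare at baseline.
- **The tables are descriptive.** They give numbers and percentages by arm in a synoptic report of a terminated study. No ratio, standard error or test is planned. In percentage points the loss is modest.

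A reader might go further and infer that spirometry as a whole is affected, or that the add-on effect is shown to be diluted. The document supports neither. Every spirometry flag except FEV1/FVC below 70% is either a change from baseline or has a change from baseline as its criterion. Dilution depends on a prevalence that is not given, and because randomization balances carried-over cases in expectation, they attenuate a contrast rather than create or reverse one.

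**Conclusion.** The point holds for absolute-threshold flags only. For those, any subject over the limit before first dose and again in the window is certain to be counted as treatment-emergent, and no summary table shows how many such subjects there are. The effect on the contrast is conditional: the risk difference falls by the factor 1 - b, so from 5.0 to 4.85 points at b = 3% and to 4.5 points at b = 10%, under the assumed new onset of 10% against 5% and equal b in both arms. The more visible effect is on interpretation, since at b = 3% over a third of the placebo cases would be carried over. It matters most for mild limits such as ALT or AST from 1 x ULN or heart rate of 50 bpm or lower, and little for severe ones. This is a reporting improvement worth making because it is cheap. It is not a flaw that undermines the safety analysis.

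**What to change.** In 9.9.3, 9.9.4 and 9.9.5, and in 9.9.6 for FEV1/FVC only, do one of the following for the absolute-threshold flags:

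1. Add a new-or-worsened row. For each category, count subjects whose on-treatment result falls in a worse category than baseline, among subjects with an on-treatment result who were not already in that category at baseline. Treat a missing baseline as new, as 5.5.11.2 does for morphology.
2. Or add a shift table from baseline to worst on-treatment category.

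Keep the present count as a separate row, labelled any on-treatment. State whether the comparison is with the derived baseline or with any pre-treatment value, since 5.5.11.2 uses the latter for morphology.

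The cost is SAP wording and one derived flag, because baseline is already flagged for these parameters. Tables become slightly longer and denominators smaller. Worsening within a category, such as ALT moving from 3.1 to 4.9 x ULN, would be seen only in the retained row and the change-from-baseline summaries.

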5.5.2 Adverse events

An AE is any event reported by the investigator on the Adverse Event eCRF of the main database or the first dose database. All AEs are coded using MedDRA dictionary (version 21.0).

5.5.2.1 Frequency and prevalence of adverse events

AEs are summarized according to both frequency and prevalence and based on various grouping terms (for example MedDRA preferred term [PT], or MedDRA primary system organ class[SOC]).

For frequency of subjects experiencing an AE, AEs reported more than once for a subject (based on grouping term) are counted only once per subject.

For total cumulative number of events, multiple records of the same MedDRA PT in the AE dataset for the same subject count as individual events (episodes of the same type of event) unless they have the same start date and – if available – time.

5.5.2.2 Intensity of adverse events

For AEs reported more than once for a subject, only the worst outcome is considered. AEs with missing severity assessment are imputed to be of ‘severe’ intensity.

5.5.2.3 Relationship of adverse events to study treatment

Relationship to study treatment is entered into the database as ‘related’ or ‘not related’. For AEs reported more than once for a subject, only the worst relationship is considered (i.e., ‘related’). AEs with missing relationship are considered to be related.

5.5.2.4 Relationship of adverse events to DMF

Relationship to DMF is entered into the database as ‘related’ or ‘not related’. For AEs reported more than once for a subject, only the worst relationship is considered (i.e., ‘related’). AEs with missing relationship are considered to be related.

5.5.2.5 Fatal adverse events

Fatal AEs are those with ‘Death’ reported as outcome.

5.5.3 Deaths

Death information (date of death and primary cause) is taken from the Death eCRF.

5.5.4 Serious adverse events

An AE is considered serious if the question ‘Serious?’ on the Adverse Event eCRF is answered with ‘Yes’. AEs with seriousness criteria missing are considered to be SAEs.

5.5.5 Adverse events leading to discontinuation of study treatment

AEs leading to discontinuation of study treatment are those with ‘Action taken with study drug’ reported as ‘Permanently discontinued’.

5.5.6 Adverse events leading to temporary interruption of study treatment

AEs leading to temporary interruption of study treatment are those with ‘Action taken with study drug’ reported as ‘Temporarily interrupted’.

5.5.7 Adverse events leading to hospitalization

AEs leading to hospitalization are those where the eCRF question ‘Did the Adverse Event require subject hospitalization?’ is recorded as ‘Yes’ on the Adverse Event eCRF.

5.5.8 Adverse events on Day 1 and Day 1 of re-initiation of study treatment

Treatment-emergent AEs on Day 1 of study treatment are those AEs that start on or after study treatment start (on Day 1), by time and date, and before the following calendar date.

Treatment-emergent AEs on Day 1 of re-initiation of study treatment are those AEs that start on the date of a study treatment re-initiation.

Note: AEs in the first dose database with a different onset date than the first study drug intake or Day 1 of re-initiation of study treatment are not considered as ‘Day 1’ / ‘Day 1 of re-initiation of study treatment’ events.

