9.9 Analysis of safety variables

9.9.1 Adverse events

All AEs captured (i.e., from signature of informed consent up to EOS) are reported in the subject listings based on the SCR, treatment-emergent events are flagged.

Unless otherwise specified, the SAF is used for all analyses of AEs.

An overview of treatment-emergent AEs is presented, per treatment group, as the number and percentage of subjects having any AE, any severe AE, any drug-related AE, any AE leading to study drug discontinuation, any SAE, any drug-related SAE, or any fatal SAE.

Also, AEs are summarized by SOC and PT: Presenting, per treatment group, the number and percentage of subjects having any AE, having an AE in each primary SOC, and having each individual AE (PT). SOC's are sorted by descending order of frequency in the ponesimod arm. If the frequencies of SOC's are the same, alphabetical order is used. The same rule applies for PT's within SOC. The following summaries are presented:

- Treatment-emergent AEs
- Treatment-emergent AEs on Day 1
- Treatment-emergent AEs on Day 1 of re-initiation, for subjects with at least one re-initiation
- Treatment-emergent AEs leading to temporary interruption of study treatment
- Treatment-emergent AEs considered to be related to DMF
- Treatment-emergent AEs considered to be related to study drug
- Treatment-emergent AEs with fatal outcome

Also, treatment-emergent AEs are summarized by PT: presenting, per treatment group, the number and percentage of subjects having any AE, and having each individual AE (PT). PT's are sorted by descending order of frequency in the ponesimod arm. If the frequencies are the same, alphabetical order is used.

For the disclosure of the results to EudraCT and ClinicalTrials.gov (and inclusion in the CSR appendix), frequent treatment-emergent non-serious AEs, i.e., PT's reported in $\geq 5\%$ of subjects in at least one treatment group, are summarized as follows:

- 1) The number and percentage of subjects having any frequent non-serious AE, and having each individual non-serious AE (PT).
- 2) The overall number of frequent non-serious AEs (i.e., reported episodes), and the number and percentage of frequent AEs (PT). Here the denominator is the overall number of frequent non-serious AEs.

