 - If the record’s origin is the First-Dose eCRF and the year is clearly after the year of STS, but a date of re-initiation with corresponding year is documented, impute onset date and time as the date and time of this re-initiation study drug intake (in case more than one study drug re-initiations are documented in this year, impute with the date and time of the earliest of those).
 - If the record’s origin is the First-Dose eCRF and the year is clearly after the year of STS, but no date of re-initiation with corresponding year is documented, the onset date is imputed to January 1st of the given year and time to 00:00.
 - If the record’s origin is the main CRF and year is clearly on or after the year of STS, the onset date is imputed as date of maximum of (Treatment Day 2, January 1st of the given year) and time is imputed to 00:00.
 - If the event onset year is clearly prior to the year of STS, the onset date is imputed to 31-December of the given year and time is imputed to 00:00. This imputation is done irrespective of eCRF origin (First-Dose or Main).
- Missing onset time is imputed to
 - the time of the STS, if the onset date equals the STS.
 - the time of the study drug intake at re-initiation, if the onset date equals the date of a documented study drug re-initiation.
 - 00:00, for any other onset date.
- Onset date is completely missing: Consider as treatment-emergent.
The onset date and time is imputed as date and time of the STS (if death date or if AE onset date with record’s origin is the First-Dose eCRF), if AE onset date with record origin in the main CRF, the onset date is imputed as Study Day 2.

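### Restart-day adverse events are selected by calendar date alone, so events that began before the restart dose are counted, unlike on Day 1

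*SAP*

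**What the plan says.** **Adverse events.** Section 5.5.8 defines Day 1 events as those that "are those AEs that start on or after study treatment start (on Day 1), by time and date, and before the following calendar date". The next sentence defines restart-day events as those that "are those AEs that start on the date of a study treatment re-initiation". The note that follows excludes first-dose-database events with a different onset date; it does not mention time. Section 9.9.1 then tabulates "Treatment-emergent AEs on Day 1 of re-initiation, for subjects with at least one re-initiation", and Section 9.9.2.2 does the same for SAEs.

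**ECG morphology.** Section 5.5.11.2 calls a finding new "if not present at any pre-treatment assessment (i.e., at any ECG assessed prior to the study treatment start"). Section 9.9.3 uses that flag to tabulate subjects with "new treatment-emergent post-dose morphological ECG findings on Day 1 or on Day 1 of any re-initiation".

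**Related rules.** Section 5.5.1 defines the pre-dose assessment on a restart day as the last non-missing one before that day's intake. Sections 5.5.10.1 and 5.5.11.1 use it for changes in blood pressure, PR and QTc after a restart dose. Section 12.3 imputes a missing AE onset time on a restart date to "the time of the study drug intake at re-initiation, if the onset date equals the date of a documented study drug re-initiation".

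**The concern.** The SAP describes the titration scheme, at first dose and at re-initiation after an interruption of more than 3 days, as a means of reducing first-dose effects (2.1.1). The separate restart-day tables let a reader see what follows a restart dose. An event with onset before that dose, after days off drug, does not belong in such a table, and the Day 1 rule would exclude it. The two tables are likely to be read side by side, although one is conditioned on the dose time and the other is not.

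The same question arises for ECG morphology. On Day 1 the pre-dose ECG is itself a pre-treatment ECG, so the flag serves the table well. On a restart day, the period between first treatment and the restart is left out of the comparison.

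**Working it through.** No sample size, power or error rate is involved, so the check follows each table back to its derivation rule and looks for any other rule that supplies the missing time reference.

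**1. AE selection, side by side**

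| Step | Day 1 | Day 1 of re-initiation |
|---|---|---|
| Lower bound in 5.5.8 | First intake, date and time | Restart date only |
| Upper bound in 5.5.8 | Before the next calendar date | Same calendar date |
| Treatment-emergent filter in 5.5.1 | Removes events before first intake where times are available | Does not act on a restart day |

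The filter does not act because it runs "on or after the study treatment start date and prior to or on the EOT date + 15 days (inclusive"). It is anchored to the first dose and the final end of treatment. An interruption does not break it, so an event just before a restart dose still qualifies as treatment-emergent.

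**2. Illustrative case.** Suppose a dose at 09:00 and AE onset at 07:00 on the same date. On Day 1 the event is excluded. On a restart day it is counted. The reverse error cannot occur: every event that starts after the restart dose on that date also satisfies the date-only rule. The AE and SAE tables can therefore only over-count.

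**3. Is a time rule workable?** Yes. Section 12.3 already relies on the restart intake time. A missing onset time on a restart date becomes the intake time. Partly dated first-dose-eCRF events that are matched to a restart are given its date and time. All of these would satisfy an at-or-after rule. A time rule would remove only events whose recorded onset time precedes the dose.

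**4. ECG morphology.** Take a finding that is absent from every pre-treatment ECG, arises during the first course of treatment, and is visible on the restart-day pre-dose ECG and again after the dose. Under 5.5.11.2 it is new, so 9.9.3 counts it among post-dose findings on the restart day, although it was there before the dose. No morphology flag against that day's pre-dose ECG is defined, even though the schedule calls for the tracing at re-initiation.

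**5. What is not affected.** Restart-day PR and QTc change flags use the same-day pre-dose value (5.5.11.1), as do the blood-pressure decrease flags (5.5.10.1). Heart-rate outliers are absolute thresholds. Day 1 itself is sound for both AEs and morphology.

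**The case against.** **Over-inclusion may be deliberate.** The SAP is conservative elsewhere: missing severity becomes severe, missing relationship becomes related, and a missing pre-treatment ECG makes a finding new. The date-only rule applies alike to both blinded arms, and the table label claims timing on a day, not causation. This limits the seriousness, but it does not explain the asymmetry. The other conventions deal with missing data, whereas this rule disregards a recorded onset time. It also sits beside a Day 1 rule that uses one: "that start on or after study treatment start (on Day 1), by time and date".

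**The pre-treatment ECG reference has a purpose.** Comparing with all pre-treatment ECGs keeps intermittent, long-standing findings from being called new. Replacing it with a single pre-dose tracing would relabel a finding documented at screening whenever that one tracing happened to miss it. This objection stands, so the existing flag should be kept and a second one added.

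**Stronger readings that a reader might infer.** One is that all restart-day safety tables use the wrong reference. The documents do not support this: the quantitative ECG and blood-pressure flags use the same-day pre-dose value.

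Another is that one misclassified subject shifts the restart-day incidence by some stated number of points. If 10% of about 68 subjects per arm re-initiated (136/2 = 68; 0.10 × 68 = 6.8, about 7), one subject would weigh 1/7, or about 14 points. At 5% (about 3 subjects) or 20% (about 14) the weight would be about 33 or 7 points. The re-initiation rate has no source in the SAP, and these figures give the weight of any one subject, not how often the rule misclassifies. The re-initiator denominator is also stated only for the AE and SAE tables. The morphology summary is based on the safety set and names Day 1 and re-initiation together; on about 68 per arm one subject would be 1/68, about 1.5 points.

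**Low consequence.** The tables are descriptive, for a synoptic report of a terminated study, and all AEs and ECG findings are also listed by subject. This stands, and the point should be ranked accordingly.

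**Conclusion.** The AE point holds. Section 5.5.8 states a restart-day rule that admits events preceding the restart dose, nothing else in the SAP removes them, and the error runs in one direction. The ECG point holds for morphology only, as a case for an additional flag. It does not show that the present definition is wrong for the overall treatment-emergent table or for Day 1.

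The number of subjects affected cannot be derived from the SAP and may be zero. No hypothesis test or efficacy endpoint is touched. The conclusion rests on reading 5.5.8 literally and assumes that at least some restart-day AEs have a recorded onset time. Where none is recorded, the corrected rule gives the same result as the present one.

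**What to change.** 1. **Section 5.5.8.** Define restart-day AEs as those with onset date and time on or after the re-initiation intake date and time and before the following calendar date, with missing onset times imputed as in Section 12.3. The tables in 9.9.1 and 9.9.2.2 then follow without further change.
2. **Sections 5.5.11.2 and 9.9.3.** Keep the existing flag. For restart days, add a flag for findings not present on that day's pre-dose ECG. Fall back to the existing flag if that ECG is missing; the deviation code list implies that post-dose monitoring is not required at every restart. Present Day 1 and re-initiation separately.

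The cost is a few sentences of SAP text, one changed selection condition and one added derived flag. The onset and intake times are already used by Section 12.3 and the pre-dose ECG is already scheduled at re-initiation, so no new data collection is needed.
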